7.1.3 Tertiary study endpoints

- Inflammatory parameters as measure for disease severity derived from whole blood (e.g. sTREM-1, procalcitonin)
- Microbiome analysis, by analysing skin swabs and comparing it with deeper cultures and blood markers
- Single Nucleotide Polymorphisms (SNP's) associated with higher disease severity, analysed in whole blood

7.2 Randomisation, blinding and treatment allocation

Patients who respond to initial therapy will be randomized in a 1:1 ratio at day 5 by the commonly used online ALEA® randomisation software to one of two arms (starting at day 6):

(A) Standard course: after 6 days of flucloxacillin, another 6 days of oral flucloxacillin.

(B) Short course: after 6 days of flucloxacillin, 6 days of oral placebo.

The independent central randomisation service will create a computer generated random schedule in permuted blocks, stratified for diabetes mellitus (yes or no) and study site. The code will only be broken in case the DSMB advises to do so.

Hospital pharmacies are closed during the weekends, but there is a possibility that patients need to be evaluated for their day 5-6 timepoint somewhere during the period between Friday 16:00, and Monday 9:00, while they also need to receive their first dose of study medication in that period. For those patients, normal randomisation would be unfit because the study medication can't be delivered in time. For this minor group of patients, a different method of randomisation is used:

- Before Friday afternoon (ideally on the day 2-3 visit), the researchers will evaluate if the patient is likely to be randomised during the weekend period. If that is the case, the default checks in the eCRF are bypassed, and the patient is preliminarily randomised, thus assigning a randomisation number, and allowing the pharmacy to prepare the appropriate medication.
- Medication for these patients will be prepared by the AMC pharmacy, even if patients are admitted to other study sites. The researchers will collect the medication and store it in their workspace.
- Upon evaluation of the patient during the day 5-6 timepoint, the researchers will judge if the patient is able to be randomised according to the randomisation criteria.
 - o If the patient **can** be randomised, the medication will be given as if the patient was randomised as normal. Data entry will be done on the same day, and the built-in eCRF checks will automatically be performed during the night, confirming the appropriate randomisation.

- If the patient **cannot** be randomised, the patient will be treated as any other person unfit for randomisation. Medication will be returned to the AMC pharmacy at the earliest convenience, for reuse if possible, and the drug accountability list entries will be undone. A form will be submitted to the Clinical Research Unit, requesting the undoing of the randomisation, to free up the used randomisation number. This way, the block randomisation will be kept intact without blocks missing patients in the end.
 - Criteria for medication reuse (such as temperature control) will be agreed upon with the pharmacy.

7.3 Study procedures

See paragraph 3.3 for an overview of when study procedures take place.

7.3.1 Baseline characteristics and physical examination

On the first day of enrolment a medical history will be obtained and a physical examination will be performed. The following disease characteristics will be collected:

- Demographic and baseline patient characteristics which might intervene with the main study parameter (confounders), including: age, gender, medication, ethnic background, recreational drug use, comorbidity (including diabetes), smoking, body weight, and residence before hospital admission (e.g. other hospital or nursing home).
- Baseline disease characteristics: cellulitis severity score, cellulitis lesion surface area (cm²)²³, presence of lymphadenopathy (axillary or inguinal), predisposing risk factors for cellulitis²⁴ (i.e. venous insufficiency, lymphoedema, peripheral arterial disease, immunosuppression, diabetes, trauma, tattoos, ulcers, eczema, tinea pedis and burns), white blood cell count and C-reactive protein (CRP). Photographs will be taken of the lesion as an illustration of the different grades used in scoring. Physical examination will be repeated at day 5-6, 14-15 and 28-29.
- Causative agents: microbiological samples for culture will be collected as aspirates, biopsies, deep swabs or other appropriate methods (superficial swabs are not acceptable) plus blood culture, according to standard of care at each center.
- Hematology and chemistry lab results will be collected through regular care.
- For the 20 healthy volunteers, only basic data such as age, gender, diabetes status and cellulitis history will be recorded.

7.3.2 Cellulitis severity score

The severity of cellulitis will be graded at day 0, 2-3, 5-6, 14-15 and 28-29 using a clinical scoring sheet, in which the investigators assign an assessment (none, mild, moderate, or severe) to each of the following parameters: erythema, warmth, tenderness, edema,

ulceration, drainage, and fluctuance. Grading of each will be standardized among investigators at the beginning of the study by simultaneous readings. The grading designations none through severe are converted into a numerical value of 0 to 3 and these numbers were added to create a physician composite score for purposes of analysis (maximum score 21). This scoring system is the same as used in the most recent therapy duration study.¹² This will allow for measuring of objective (investigator-evaluated) improvement.

Two investigators (the PhD student and the trial nurse) will be responsible for data collection throughout the study. To minimize inter-observer variation and to promote data quality, initial patient assessment will be performed simultaneously by both investigators, and later independently and scores compared/evaluated. When five patients have been assessed independently, resulting in identical scores from both investigators, the investigators will start assessing patients on their own. After 100 patients have been assessed by a single investigator, the investigators will again assess five patients together, to compare scoring and thus improve data quality. During the course of the trial it will be evaluated if additional investigators need to be recruited, due to possible heavy workload and time spent on traveling between sites. Additional investigators will be trained by the PhD student in similar fashion as the trial nurse, with simultaneous and subsequent independent scoring as described above.

Patient self assessment scores will be performed at day 0, 2-3, 5-6, 14-15, 28-29 and 90 by visual Analog Scales (VAS) scores (rated 0-10) in order to determine the amount of pain and swelling patients experience accounting for subjective (patient-evaluated) improvement.

7.3.3 Quality of life

The Dutch SF-36 questionnaire will be used to assess health-related Quality of Life. This will be performed at inclusion and after 28-29 and 90 days. The SF-36 is a validated questionnaire²⁵, allowing the study population to be compared with equivalent controls in the general Dutch population.

7.3.4 Health care associated costs

Patient information on antibiotic use and health care utilization for cellulitis related complaints (e.g. outpatient services, inpatient admissions, other health care provider services, use of antibiotics and other medication, assist devices or materials) will be collected at certain intervals. This will be collected through Health Care Utilization Questionnaires and patient records at days 5-6, 28-29 and 90. Parallel to this analysis, the EQ-5D-3L questionnaire will be utilized to index the health state of the patients and to accentuate the cost utility analysis.

7.3.5 Blood samples

At day 0, 2-3, 5-6, 14-15 and 28-29 blood will be drawn in order to assess inflammatory markers in blood. This will require extra venous punctures. Up to 42 ml of blood can be taken each visit, adding up to a total of 83,5 ml for non-AMC patients and 99,5 ml for AMC patients (see table for accurate ml per day). Ten (10) ml of EDTA plasma will mainly be

used for measurement of biomarkers and cytokines associated with the inflammatory process, but an extra 10 ml EDTA plasma will be taken from AMC patients on day 0, to be used for RNA and protein analysis in polymorphonuclear (PMN) leukocytes. This will only be done in AMC patients and only on day 0, due to time constraints (preparation for storage of these samples using Ficoll takes several hours and has to be done soon after collection from the patient). After March 30th 2017, no more extra blood will be taken from AMC patients.

Citrated blood will be used to analyze parameters of coagulation that have yet to be determined. An additional PAXgene tube will be taken to be able to isolate RNA from peripheral whole blood leukocytes. To associate certain SNP's in genes encoding for yet to be determined markers (f.e. complement factors), with disease severity and/or outcome, an extra 4,5ml EDTA tube will be collected. Samples will be processed on the day of collection, and stored in -20°C or -80°C (as needed), for analysis at the time that all samples have been collected.

7.3.6 Skin swabs

Using kits bought from Microbiome (Houten, NL), we will explore possible new diagnostic options. Currently, blood cultures and skin cultures are negative more often than not, and (at least for skin cultures) culture results are not always reliable due to uncertainty of contamination. From each patient we'll collect skin swabs (one on the affected limb, one on the contralateral limb), and culture results, and we will process a selected number of skin biopsies for microbiota analysis (protocol is drawn up in collaboration with Microbiome). For a limited number of patients, swabs will be collected from the other limb on day 1 as well (so in case of cellulitis of the leg, swabs will also be taken from each arm), to a total of 4 swabs. After March 9th 2017, no more swabs will be taken from new patients.

From 20 healthy volunteers, which are age- and gender-matched to the population of swabbed patients, one swab will be taken from a(n unaffected) lower leg.

	Volume	Day 0	Day 2-3	Day 5-6	Day 14-15	Day 28-29
Blood						
EDTA tube 10 ml each)	10 ml*	1 tube (AMC: +1)	1 tube	1 tube	1 tube	1 tube
Citrated tube (4.5 ml each)	4,5 ml	2 tubes			2 tubes	
PAXgene tube (2.5 ml each)	2.5 ml	1 tube			1 tube	
EDTA tube for DNA (4,5 ml each)	4,5 ml	1 tube				
Microbiome analysis						
Skin swab	swab	2-4			2 swabs	

	swabs				
Total	26 ml -	10 ml	10 ml	21.5 ml	10 mL
	36 ml				
Skin biopsy	4 mm	3			

* Depending on study location; AMC patients will have 20 ml taken on the first day, while others have 10 ml taken. The reason for this, is that the extra 10ml takes a lot of time to process, and therefore cannot be done for every patient. Seeing how the quality of this particular sample depends on the time between drawing the blood and processing it, the AMC patients are the best candidates for the best samples. Total blood drawn during the course of the study will thus be 87.5 ml from AMC patients, and 77.5 ml from non-AMC patients. After March 30th 2017, no more extra blood will be taken from AMC patients.

All variables that are going to be analyzed will be on a pre-clinical level and will be of no consequence for individual patients. Only the aggregated information on group level will be important.

7.3.7 Skin biopsies

Skin biopsies will be performed on patients admitted to the AMC (not to other study centers, due to logistic reasons), for use in future studies of the pathobiology of cellulitis. Specific consent will be obtained for the collection of these biopsies. On the day of enrolment, two biopsies (4mm in diameter) will be taken from the afflicted area plus one biopsy (4 mm in diameter) from the contralateral unaffected limb. The majority of the biopsy samples will be formalin fixed and paraffin embedded, or snap-frozen. The formalin-paraffin samples will be used for pathological (immuno)staining, the frozen samples will be used for isolation of mRNA for inflammatory array analysis, selected inflammatory parameters, or microbiome analysis. Additional in-depth immunological analyses can be decided upon during the course of the study.

A deep skin culture will be taken from the biopsy site during the biopsy procedure.

After March 30th 2017, no more skin biopsies will be taken.

7.4 Withdrawal of individual subjects

Subjects can leave the study at any time for any reason if they wish to do so without any consequences. The investigator can decide to withdraw a subject from the study for urgent medical reasons.

7.5 Replacement of individual subjects after withdrawal

Not applicable, an intention-to-treat analysis will be performed.

7.6 Follow-up of subjects withdrawn from treatment

As per usual care, they might receive an antibiotic treatment schedule at the discretion of their attending physician.

7.7 Premature termination of the study

The sponsor has the right to terminate the study prematurely if there are any relevant medical or ethical concerns, or if completing the study is no longer feasible. If such action is taken, the reasons for terminating the study must be documented. All study subjects still under treatment at the time of termination must undergo a final examination, which must be documented. The METC must be informed without delay if any investigator has ethical concerns about continuation of the trial.

Premature termination of the trial will be considered if:

- The risk-benefit balance for the study subjects changes markedly;
- It is no longer ethical to continue with the shorter duration of antibiotics strategy, as decided by the DSMB;
- It is no longer feasible to complete the study.

8. SAFETY REPORTING

8.1 Section 10 WMO event (temporary halt for reasons of subject safety)

In accordance to section 10, subsection 4, of the WMO, the sponsor will suspend the study if there is sufficient ground that continuation of the study will jeopardise subject health or safety. The sponsor will notify the accredited METC without undue delay of a temporary halt including the reason for such an action. The study will be suspended pending a further positive decision by the accredited METC. The investigator will take care that all subjects are kept informed.

8.2 AEs, SAEs and SUSARs

8.2.1 Adverse events (AEs)

Adverse events are defined as any undesirable experience occurring to a subject during the study, whether or not considered related to the investigational product or experimental interventions. All adverse events, reported by the subject or observed by the investigators, meeting all of the following criteria will be recorded:

- Severity: grade 2, or grade 1 lasting longer than 1 week, graded by the CTCAE (Common Terminology Criteria for Adverse Events, v4.03, June 2010)
- Causality: there needs to be a reasonable suspicion of the AE being an effect of the medical treatment
- Time window: between the moment of inclusion and the day 28 follow-up visit

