8.2.2 Serious adverse events (SAEs)

A serious adverse event is any untoward medical occurrence or effect that at any dose:

- results in death;
- requirement of hospitalisation or prolongation of existing inpatients' hospitalisation for reasons not related to cellulitis
- is life threatening (at the time of the event);
- results in persistent or significant disability or incapacity;
- is a congenital anomaly or birth defect;
- any other important medical event that may not result in death, be life threatening, or require hospitalization, may be considered a serious adverse experience when, based upon appropriate medical judgement, the event may jeopardize the subject or may require an intervention to prevent one of the outcomes listed above.

The sponsor will report the SAEs through the web portal *ToetsingOnline* to the accredited METC that approved the protocol, within 15 days after the sponsor has first knowledge of the serious adverse reactions. This holds true for both the coordinating center as well as the participating centers (see PIs as stated above).

SAEs that result in death or are life threatening should be reported expedited. The expedited reporting will occur not later than 7 days after the responsible investigator has first knowledge of the adverse reaction. This is for a preliminary report with another 8 days for completion of the report.

Of note, since a significant part of included patients is expected to be readmitted to the hospital due to relapse of cellulitis, the requirement of hospitalisation or prolongation of existing inpatients' hospitalisation due to cellulitis is not considered a SAE and will not be reported to the METC but will be subjected by monitoring by the DSMB. SAE's will be reported until the patient reaches the end of study. To facilitate SAE reporting in the period between day 28 and day 90, participants will receive a card on day 28 with instructions to contact the study team in case any SAE occurs.

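### Read literally, the AE rule in section 8.2.1 omits non-serious events of grade 3 or higher, and non-serious events not attributed to treatment

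*Combined protocol and SAP*

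**What the plan says.** Section 8.2.1 starts from a broad definition: an adverse event is any undesirable experience during the study, "whether or not considered related to the investigational product or experimental interventions". It then restricts what is entered: "All adverse events, reported by the subject or observed by the investigators, meeting all of the following criteria will be recorded". Three criteria follow.

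- Severity: the line reads "Severity: grade 2, or grade 1 lasting longer than 1 week, graded by the CTCAE" (version 4.03).
- Causality: "there needs to be a reasonable suspicion of the AE being an effect of the medical treatment". The term for the treatment is not defined.
- Time window: "between the moment of inclusion and the day 28 follow-up visit".

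Section 8.2.2 provides a second route, for serious events. It opens "A serious adverse event is any untoward medical occurrence or effect that at any dose" and lists outcomes that make an event serious, including a category left to medical judgement. It sets no grade threshold and requires no causal link, and reporting runs to the end of the patient's participation. Hospital admission for cellulitis is excluded from the SAE definition and assigned to DSMB monitoring.

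**The concern.** There are two separate problems.

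First, the severity line names grade 2 and prolonged grade 1 and stops there. Because all criteria must be met, a grade 3 event fails the rule that a grade 2 event passes. That ordering can hardly be intended, but site staff and eCRF checks follow what is written.

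Second, the causality criterion makes a judgement of relatedness a condition for entering the event at all. An event screened out at the bedside cannot be reclassified later, and assessors may differ on what counts as an effect of the treatment when the term is undefined.

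The AE record has uses elsewhere in the plan. Section 10.4 cites antibiotic side effects as a reason for shortening therapy. Section 8.3 promises a full safety analysis and a weighing of efficacy against harm. Section 7.7 makes a marked change in the risk-benefit balance a ground for considering termination. Section 9.1 counts inability to complete because of adverse events as a clinical failure in the per protocol analysis of the primary outcome. An incomplete AE record weakens each of these.

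**Working it through.** The plan states no figure to reproduce on this point, so the check applies the rule as worded and then traces what it drops.

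**Step 1: the rule as logic.** An event is recorded as an AE if (grade = 2, or grade = 1 and duration over 1 week) and a treatment effect is suspected and it falls between inclusion and the day 28 visit. For an event inside the window:

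| CTCAE grade | Duration | Treatment effect suspected | Not suspected |
|---|---|---|---|
| 1 | up to 1 week | not recorded | not recorded |
| 1 | over 1 week | recorded | not recorded |
| 2 | any | recorded | not recorded |
| 3, 4, 5 | any | not recorded | not recorded |

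Grades 3 to 5 fail on severity whatever the duration or suspected cause. Events not attributed to treatment fail at every grade. No other section widens the grade range for non-serious events.

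**Step 2: where the dropped events could still appear.**

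- Non-resolution at day 14-15 and recurrence by day 28-29 form the primary endpoint (7.1.1). Recurrence by day 90 is a secondary endpoint (7.1.2).
- Local worsening is scored up to day 28-29 (7.3.2).
- Cellulitis-related care, admissions and antibiotic use are collected at days 5-6, 28-29 and 90 (7.3.4). Readmissions are also asked about by telephone at day 90 (11.1).
- Serious events are SAEs regardless of cause (8.2.2).
- Reasons for non-adherence are recorded (5.4), and antibiotics received after discharge are collected from the patient (11.1). These may reveal some other events indirectly.

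**Step 3: what remains without an AE route.** (a) Suspected treatment reactions of grade 3 or higher that are not judged serious. (b) Other non-serious events, such as those unrelated to cellulitis, that are not attributed to treatment. The questionnaire in 7.3.4 is confined to cellulitis-related complaints, so it is no general substitute.

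**Step 4: size.** The documents give no AE rate by grade. The one rate stated is in section 6.4: the most frequent side effects of flucloxacillin occur in 0.1-1% of patients. With 158 per arm (section 4.4), that is 0.001 × 158 = 0.16 to 0.01 × 158 = 1.58 patients per arm. This covers the commonest drug effects without restriction by grade. It is neither an estimate nor a bound for (a) or (b).

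**Step 5: a related mismatch.** Section 11.1 lists adverse events among the information collected at day 90, whereas the window in 8.2.1 closes at day 28.

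**The case against.** The strongest reply on severity is that the line is shorthand for a floor. A rule that admits long-lasting grade 1 events reads naturally as a minimum, and a comparison sign may have been lost when the PDF was converted: the Summary gives age as above 18, while section 4.2 says 18 or older. This is plausible but not shown. If the PDF carries the sign, the severity point falls and the causality point remains.

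The reply on causality is that defining AEs broadly and recording a subset is a legitimate scoping choice for an authorised product, and that the discretionary SAE category can take in some severe events. Both stand in part: this is an awkward fit with the definition more than a flat contradiction. But the discretionary category turns on seriousness, not grade, and nothing states where the remaining non-serious events go.

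A reader might infer that the harms of stopping early go unrecorded. The documents do not support that, because the main ones are the trial's endpoints and the serious ones are SAEs.

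A reader might also infer that the causality criterion tilts the record towards harm in the 12-day arm. That is not shown. Patient, physician and observer are blinded (3.1), both arms receive six days of flucloxacillin (5.1), and the AE window opens at inclusion, before randomisation. AEs are not an endpoint and have no row in Table 3, so no planned between-arm comparison of them exists to be distorted.

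**Conclusion.** The point holds in limited form. As worded, section 8.2.1 gives no AE route to non-serious suspected reactions of grade 3 or higher, or to non-serious events not attributed to treatment and not otherwise captured as endpoints or study data. The first part assumes the severity line is complete as it stands; the second does not depend on that.

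The number of events affected cannot be estimated. A reader might put a rate on them: an assumed 1-5% of 158 gives 1.6 to 7.9 patients per arm. Nothing in the documents supports that assumption. The primary analysis is not affected. What is affected is the completeness of the safety record, and events never entered may not be recoverable later. The correction is worth making because it is cheap.

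**What to change.** Check the severity line against the source PDF. Unless it already says so, state the threshold as grade 2 or higher, or grade 1 persisting beyond one week.

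Remove causality as a condition for recording. Add a relatedness field to the eCRF, completed for every recorded event under the existing blind, with a definition of what the medical treatment covers.

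In the same amendment, reconcile the day 28 window in 8.2.1 with the day 90 collection of adverse events in 11.1.

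The cost is a few amended lines, one eCRF field and somewhat more AE data entry up to day 28. Visits, sample size and the primary analysis are unchanged.
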